3.3 DOSE DELAYS/MODIFICATIONS

Any toxicity observed during the course of the study could be managed by interruption of the dose of study treatment or dose reductions. Repeat dose interruptions are allowed as required, for a maximum of 4 weeks on each occasion. Study treatment can be modified per Table 2. If the reduced dose of 200 mg twice daily is not tolerable, no further dose reduction is allowed and study treatment should be discontinued.

Once dose is reduced, escalation is not permitted.

Table 2: Dose levels for olaparib dose modification

| Dose Level | Olaparib tablets |
|-------------------------|--------------------|
| 1 (Starting dose level) | 300 mg twice daily |
| -1 | 250 mg twice daily |
| -2 | 200 mg twice daily |

3.3.1 Modifications and Management of Hematologic Toxicities

3.3.1.1 Anemia

| Table 3: Dos | se Delay/Mo | odification | and Manager | nent of Anemia |
|--------------|-------------|-------------|-------------|----------------|
| | •/ | | | |

| Hemoglobin | Action to be taken |
|-----------------------------|--|
| $Hb < 9 \ but \ge 8 \ g/dL$ | Give appropriate supportive treatment and investigate causality. |
| | Investigator judgment to continue olaparib with supportive treatment (e.g. transfusion) or interrupt dose for a maximum of 4 weeks. |
| | If repeat Hb < 9 but \ge 8 g/dL, dose interrupt (for max of 4 weeks) until Hb \ge 9 g/dL and upon recovery dose reduction to 250 mg twice daily as a first step and to 200 mg twice daily as a second step may be considered. |
| Hb < 8 g/dL | Give appropriate supportive treatment (e.g. transfusion) and |
| (CTCAE Grade 3) | investigate causality. |
| | Interrupt olaparib for a maximum of 4 weeks. until improved to Hb \geq 9 g/dL. |
| | Upon recovery dose reduce to 250 mg twice daily as a first step and to 200 mg twice daily as a second step in the case of repeat Hb decrease. |

Common treatable causes of anemia (e.g., iron, vitamin B12 or folate deficiencies and hypothyroidism) should be investigated and appropriately managed. In some cases, management of anemia may require blood transfusions. For cases where patients develop prolonged hematological toxicity (\geq 2-week interruption/delay in study treatment due to CTCAE grade 3 or worse anemia and/or development of blood transfusion dependence), refer to Section 3.3.1.3 for the management of this.

3.3.1.2 Neutropenia, Leukopenia and Thrombocytopenia

| 1 momboey topenia | |
|-------------------|--|
| Toxicity | Study treatment dose adjustment |
| CTCAE Grade 1-2 | Investigator judgment to continue treatment or if dose interruption, this should be for a maximum of 4 weeks; appropriate supportive treatment and causality investigation |
| CTCAE Grade 3-4 | Dose interruption until recovered to CTCAE gr 1 or better for a maximum of 4 weeks. If repeat CTCAE grade 3-4 occurrence, dose reduce olaparib to 250 mg twice daily as a first step and 200 mg twice daily as a second step |

| Table | 4: | Dose | Modification | and | Management | of | Neutropenia, | Leukopenia | and |
|-------|-----|---------|--------------|-----|------------|----|--------------|------------|-----|
| Throm | boc | ytopeni | ia | | | | | | |

Adverse event of neutropenia and leukopenia should be managed as deemed appropriate by the investigator in consultation with the NIH CC pharmacy with close follow up and interruption of study drug if CTCAE grade 3 or worse neutropenia occurs.

Primary prophylaxis with Granulocyte colony-stimulating factor (G-CSF) is not recommended, however, if a patient develops febrile neutropenia, study treatment should be stopped and appropriate management including G-CSF should be given according to local hospital guidelines. Please note that G-CSF should not be used within at least 24 hours after the last dose of and within 24 hours (14 days for pegylated G-CSF) before resuming study treatment unless absolutely necessary.

Platelet transfusions, if indicated, should be done according to local hospital guidelines.

For cases where patients develop prolonged hematological toxicity (≥ 2 -week interruption/delay in study treatment due to CTCAE grade 3 or worse), refer to Section 3.3.1.3.

3.3.1.3 Management of Prolonged Hematological Toxicities while on Study Treatment

If a patient develops prolonged hematological toxicity such as:

- ≥2-week interruption/delay in study treatment due to CTCAE grade 3 or worse anemia and/or development of blood transfusion dependence
- ≥2-week interruption/delay in study treatment due to CTCAE grade 3 or worse neutropenia (ANC < 1000/mcL)
- ≥2-week interruption/delay in study treatment due to CTCAE grade 3 or worse thrombocytopenia and/or development of platelet transfusion dependence (Platelets < 50,000/mcL)

Check weekly differential blood counts including reticulocytes and peripheral blood smear. If any blood parameters remain clinically abnormal after 4 weeks of dose interruption, the patient should be referred to hematologist for further investigations. Bone marrow analysis and/or blood cytogenetic analysis should be considered at this stage according to standard hematological practice. Study treatment should be discontinued if blood counts do not recover to CTCAE grade 1 or better within 4 weeks of dose interruption.

Development of a confirmed myelodysplastic syndrome or other clonal blood disorder should be reported to the manufacturer as an SAE and full reports must be provided by the investigator to AstraZeneca Patient Safety. Olaparib treatment should be discontinued if patient's diagnosis of MDS and/or AML is confirmed.

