2 ELIGIBILITY ASSESSMENT AND ENROLLMENT

2.1 ELIGIBILITY CRITERIA

- 2.1.1 Inclusion Criteria
- 2.1.1.1 Patients must have histologically or cytologically malignant mesothelioma confirmed by the NCI Laboratory of Pathology. Patients with pleural, peritoneal, pericardial or tunica vaginalis mesothelioma are eligible.
- 2.1.1.2 Archival tumor samples must be available and sufficient for diagnostic and genetic testing; if archival sample insufficient for testing, subject must have lesions amenable to biopsy and be willing to undergo biopsy.
- 2.1.1.3 Patients must have measurable disease, as defined in sections 6.4.1 and 6.4.2.
- 2.1.1.4 Patients must have progressive disease at study entry
- 2.1.1.5 Patients must have received prior platinum and pemetrexed based therapies. Response to platinum is not an eligibility criterion for enrollment.
- 2.1.1.6 Age ≥18 years. Because no dosing or adverse event data are currently available on the use of olaparib in patients <18 years of age, children are excluded from this study, but may be eligible for future pediatric trials.
- 2.1.1.7 ECOG performance status ≤ 1 (see Appendix A).
- 2.1.1.8 Patients must have a life expectancy of ≥ 16 weeks
- 2.1.1.9 Patients must have adequate organ and marrow function ≤5days prior to C1D1 as defined below:

| leukocytes | ≥3,000/mcL |
|---------------------------|---|
| absolute neutrophil count | \geq 1,500/mcL without growth factor support |
| platelets | ≥100,000/mcL |
| hemoglobin | \geq 10 g/dL with no blood transfusion in the past 28 days |
| total bilirubin | ≤1.5 x ULN (unless Gilbert's Disease) |
| AST(SGOT)/ALT(SGPT) | \leq 2.5 X institutional upper limit of normal (\leq 5X ULN in the presence of liver metastases) |
| creatinine clearance | \geq 51 mL/min (calculated using the -Cockcroft-Gault formula . |

- 2.1.1.10 Pre-clinical data indicate that olaparib can have adverse effects on embryofetal survival and development. It is further not known whether olaparib or its metabolites are found in seminal fluid. For these reasons:
 - 2.1.1.10.1 **Women** of childbearing potential and their partners, who are sexually active, must agree to the use of 2 highly effective forms of contraception in combination (male condom plus one of the methods listed in section 2.1.1.10.3) or must totally/truly

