6.5 TOXICITY CRITERIA

The following adverse event management guidelines are intended to ensure the safety of each patient while on the study. The descriptions and grading scales found in the revised NCI Common Terminology Criteria for Adverse Events (CTCAE) version 5.0 will be utilized for AE reporting. All appropriate treatment areas should have access to a copy of the CTCAE version 5.0. A copy of the CTCAE version 5.0 can be downloaded from the CTEP web site (http://ctep.cancer.gov/protocolDevelopment/electronic_applications/ctc.htm).

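### For prolonged anemia, Table 3 and section 3.3.1.3 set recovery criteria on different scales, and the protocol does not say which one governs restart or discontinuation.

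*Combined protocol and SAP*

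**What the plan says.** Section 3.3.1.1, Table 3, covers hemoglobin below 8 g/dL, which it labels CTCAE grade 3. The instruction is "Interrupt olaparib for a maximum of 4 weeks. until improved to Hb" of at least 9 g/dL, followed by "Upon recovery dose reduce to 250 mg twice daily as a first step". Recovery is therefore an absolute hemoglobin value, and its consequence is a restart.

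The text under Table 3 turns to prolonged cases and tells the reader to "refer to Section 3.3.1.3 for the management of this". Section 3.3.1.3 defines the anemia trigger as "≥2-week interruption/delay in study treatment due to CTCAE grade 3 or worse anemia and/or development of blood transfusion dependence". It then gives the stop rule: "Study treatment should be discontinued if blood counts do not recover to CTCAE grade 1 or better within 4 weeks of dose interruption".

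For neutropenia, leukopenia and thrombocytopenia at grade 3-4, Table 4 in section 3.3.1.2 says "Dose interruption until recovered to CTCAE gr 1 or better for a maximum of 4 weeks". That is the same scale as 3.3.1.3.

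On grading, section 6.5 states that "Common Terminology Criteria for Adverse Events (CTCAE) version 5.0 will be utilized for AE reporting". The protocol does not reproduce the hemoglobin limits of the scale, apart from the grade 3 label at 8 g/dL in Table 3.

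**The concern.** One event, one drug and one 4-week window carry two definitions of recovery. The first is in g/dL and leads to restart. The second is a CTCAE grade and, if not met, leads to discontinuation. The cross-reference joins the sections without saying that one threshold overrides the other.

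Both rules sit inside section 3.3, and section 3.5.1 makes unacceptable toxicity as defined in section 3.3 a ground for removal from protocol therapy. For these patients the removal criterion therefore has two possible readings. At stake are patient safety and consistent handling: two patients with the same hemoglobin course could be managed differently, with different time on treatment. Anemia is also the most frequent serious event listed in section 13.1.3.1 (143 reports), so the rule covers a recognised toxicity of the drug.

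**Working it through.** The plan gives no figure to reproduce, so the check compares the two rules and works through the cases.

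**Inputs**

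| Item | Content | Source |
|---|---|---|
| Restart threshold | Hb at least 9 g/dL, within 4 weeks | Table 3, section 3.3.1.1 |
| Stop threshold | Not at grade 1 or better within 4 weeks | Section 3.3.1.3 |
| Trigger for 3.3.1.3 | Interruption of 2 weeks or more for grade 3 or worse anemia, and/or transfusion dependence | Sections 3.3.1.1 and 3.3.1.3 |
| Only anemia grade limit printed | Hb below 8 g/dL is grade 3 | Table 3 |
| Other blood counts | Grade 1 or better within 4 weeks | Table 4, section 3.3.1.2 |

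**Condition for a collision.** Let L be the lower hemoglobin limit of CTCAE grade 1 anemia.

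- Table 3 permits restart when Hb ≥ 9.
- Section 3.3.1.3 calls for discontinuation when Hb < L at the end of the 4 weeks.
- Both apply together when 9 ≤ Hb < L. The band is L − 9 wide if L is above 9, and empty otherwise.

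**Range for L.** L is an assumption, because the documents do not print it. They label only Hb below 8 as grade 3, which puts L above 8. The entry criterion in 2.1.1.9 requires hemoglobin of at least "10 g/dL with no blood transfusion in the past 28 days", and exclusion 2.1.2.9 bars persistent toxicity of grade 2 or worse from earlier cancer therapy. Together these suggest, but do not prove, that L is at most 10.

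| Assumed L (g/dL) | Hb at week 4 with opposite instructions | Band width (g/dL) |
|---|---|---|
| 9 or below | none | 0 |
| 9.5 | 9.0 to below 9.5 | 9.5 − 9 = 0.5 |
| 10 | 9.0 to below 10 | 10 − 9 = 1.0 |

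**Example, assuming L = 10.** Hemoglobin falls to 7.5, dosing is held, and the value at week 4 is 9.5. Table 3: 9.5 ≥ 9, so recovered, and restart at a reduced dose. Section 3.3.1.3: 9.5 < 10, so not grade 1, and discontinue.

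**Timing.**

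- Before 2 weeks, without transfusion dependence, Table 3 applies alone and there is no conflict.
- Once 3.3.1.3 applies but before week 4, its recovery window is still open, so it does not yet call for discontinuation. It is unclear, though, whether a patient at Hb 9 may restart under Table 3 or must wait for grade 1.
- At the 4-week limit the two instructions collide directly, if L is above 9.

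**Comparison with the other counts.** Table 4 and section 3.3.1.3 use the same criterion over the same 4 weeks, so only anemia has two.

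**The case against.** The best defence is the routing sentence under Table 3. It sends exactly these cases to 3.3.1.3, and a natural reading is a general rule followed by a specific rule for prolonged toxicity. That has weight: the sections are linked, and a careful reader might settle the matter that way. But the sentence only refers the reader on. It does not say that the 9 g/dL threshold stops applying, and Table 3 allows up to 4 weeks at that threshold without any exception from week 2.

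The second defence is that the collision depends on a limit the protocol does not print. This stands, and it is why the conclusion is conditional. It does not remove the defect, because nothing in the document shows that the two criteria coincide.

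Four stronger readings are tempting but not supported.

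- **Every grade 3 anemia interruption is affected.** It is not. Section 3.3.1.3 needs an interruption of at least 2 weeks or transfusion dependence.
- **Opposite instructions apply throughout weeks 2 to 4.** They do not. The stop rule bites only when the 4 weeks have run out; until then there is ambiguity.
- **The choice of rule decides who is evaluable for response.** Section 10.3.2 requires at least 50% of doses per cycle, and cycles are 21 days. A 28-day hold spread over two cycles leaves at least 28/2 = 14 held days in one of them, and 14/21 = 67%; spread over three, it covers a whole cycle. If held doses count as not taken, such a patient fails the criterion under either rule. Section 3.5.2 also keeps patients who stop treatment in follow-up for progression.
- **The 143 reports indicate how many patients here would be affected.** They come from a programme-wide olaparib/placebo database in which 1% is about 36 patients, so 143/36 is roughly 4%. They count serious events, not anemia holds of 2 weeks or more.

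**Conclusion.** Wrong as written: an internal inconsistency in a stop/restart rule, confined to prolonged anemia. Two recovery criteria on different scales cover the same 4-week window, and the cross-reference does not rank them. If the grade 1 limit L is 9 g/dL or below, the inconsistency is one of wording only. If L is above 9, patients at the 4-week limit with hemoglobin from 9 to below L receive opposite instructions, a band of 0.5 g/dL at L = 9.5 and 1 g/dL at L = 10. Whether restart at 9 g/dL is allowed earlier, once 3.3.1.3 applies, is also unclear. L is an assumption throughout. The documents do not allow an estimate of how many of the at most 40 patients would be affected. The point bears on patient safety and consistent time on treatment; it changes no sample size, error rate or planned analysis. It takes no view on which threshold is clinically right.

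**What to change.** Sections 3.3.1.1 (Table 3) and 3.3.1.3 must be reconciled:

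- give anemia one recovery criterion, in the same units in both places; if it is a CTCAE grade, print the limit in g/dL beside it;
- state which section governs once an interruption reaches 2 weeks or transfusion dependence develops, and whether restart is allowed before week 4 in those cases.

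The clinical team must choose the criterion. The cost is a protocol clarification, with no additional patients, data or analyses.

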3.3.2 Modifications and Management of Non-Hematologic Toxicities

Repeat dose interruptions are allowed as required, for a maximum of 4 weeks on each occasion. Where toxicity reoccurs following re-challenge with study treatment, and where further dose interruptions are considered inadequate for management of toxicity, then the patient should be considered for dose reduction or must permanently discontinue study treatment.

Study treatment can be dose reduced per Table 2. Treatment must be interrupted if any NCI-CTCAE grade 3 or 4 adverse event occurs which the investigator considers to be related to administration of study treatment.

3.3.2.1 Management of new or worsening pulmonary symptoms

If new or worsening pulmonary symptoms (e.g., dyspnea) or radiological abnormalities occur in the absence of a clear diagnosis, an interruption in study treatment dosing is recommended and further diagnostic workup (including a high-resolution CT scan) should be performed to exclude pneumonitis.

Following investigation, if no evidence of abnormality is observed on CT imaging and symptoms resolve, then study treatment can be restarted, if deemed appropriate by the investigator. If significant pulmonary abnormalities are identified, these need to be discussed with the Study Physician.

3.3.2.2 Management of nausea and vomiting

Events of nausea and vomiting are known to be associated with olaparib treatment. In study D0810C00019 nausea was reported in 71% of the olaparib treated patients and 36% in the placebo treated patients and vomiting was reported in 34% of the olaparib treated patients and 14% in the placebo treated patients. These events are generally of mild to moderate (CTCAE grade 1 or 2) severity, intermittent and manageable on continued treatment. The first onset generally occurs in the first month of treatment for nausea and within the first 6 months of treatment for vomiting. For nausea, the incidence generally plateaus at around 9 months, and for vomiting at around 6 to 7 months.

No routine prophylactic anti-emetic treatment is required at the start of study treatment; however, patients should receive appropriate anti-emetic treatment at the first onset of nausea or vomiting and as required thereafter, in accordance with local treatment practice guidelines. Alternatively, olaparib tablets can be taken with a light meal/snack (e.g. 2 pieces of toast or a couple of biscuits).

As per international guidance on anti-emetic use in cancer patients (ESMO, NCCN), generally a single agent antiemetic should be considered e.g. dopamine receptor antagonist, antihistamines or dexamethasone.

3.3.2.3 Renal impairment

If subsequent to study entry and while still on study therapy, a patient's estimated CrCl falls below the threshold for study inclusion (\geq 51 mL/min), retesting should be performed promptly.

A dose reduction is recommended for patients who develop moderate renal impairment (calculated creatinine clearance by Cockcroft-Gault equation of between 31 and 50 mL/min) for any reason during the course of the study: the dose of olaparib should be reduced to 200mg twice daily.

Because the CrCl determination is only an estimate of renal function, in instances where the CrCl falls to between 31 and 50 mL/min, the investigator should use his or her discretion in determining whether a dose change or discontinuation of therapy is warranted.

Olaparib has not been studied in patients with severe renal impairment (creatinine clearance \leq 30 mL/min) or end-stage renal disease; if patients develop severe impairment or end stage disease is it recommended that olaparib be discontinued.

3.3.2.4 Interruptions for intercurrent non-toxicity related events

Study treatment dose interruption for conditions other than toxicity resolution should be kept as short as possible.

All dose reductions and interruptions (including any missed doses), and the reasons for the reductions/interruptions are to be recorded in the eCRF.

Study treatment should be stopped at least 3 days prior to planned surgery. After surgery study treatment can be restarted when the wound has healed. No stoppage of study treatment is required for any needle biopsy procedure.

Study treatment should be discontinued for a minimum of 3 days before a patient undergoes radiation treatment. Study treatment should be restarted within 4 weeks as long as any bone marrow toxicity has recovered.

Because the AEs related to olaparib may include asthenia, fatigue and dizziness, patients should be advised to use caution while driving or using machinery if these symptoms occur.

| weather, etc. | | | | | | | |
|---------------------------|------------------------|----------|-------|-------|----------------------|------------------------------------|-----------------|
| | | | Cyc | le 1 | Subsequent Cycles | Treatment | Post Therapy |
| Procedure | Screening ¹ | Baseline | Day 1 | Day 8 | Day 1 | discontinuation visit ² | Follow-up |
| Informed consent | Х | | | | | | |
| Demographics | | | | | | | |
| Medical and surgical | × | | × | | | X | |
| history | | | ** | | | 4 | |
| Prior cancer therapies | λ | | | | | | |
| including radiotherapy | \mathbf{V} | | | | | | |
| History of blood | Δ | | | | | | |
| transfusions ³ | V | | | | | | |
| Inclusion exclusion | X | | | | | | |
| criteria | \mathbf{v} | | | | | | |
| Physical exam | Х | | Х | | | | |
| Vital signs | Х | | Х | | | Х | |
| Performance Score | Х | | Х | | Х | | |
| Archival or fresh tissue | Λ | | | | | | |
| for dx confirmation | V | | | | | | |
| $Labs^{4}$ | | | | | | | |
| Full hematology | Х | | Х | Х | X | X | |
| assessment ² | | | | | | 4 | |
| Biochemistry ⁶ | X | | X | X | X | X | |

Version Date: 02/24/20

Abbreviated Title: Ph 2 Olaparib in Mesothelioma

3.4 STUDY CALENDAR

1 cycle =21 days

Screening assessments must occur within 28 days prior to enrollment unless otherwise indicated. If screening/baseline assessments are performed within 7 days prior to dosing, these assessments do not need to be repeated on C1D1 unless otherwise indicated.

Assessments after and including C1D1 may be performed up to 3 days prior to indicated time unless otherwise indicated.

Dosing cycles after cycle 1 may be delayed for up to two weeks to accommodate schedule conflicts. Federal holidays and inclement

| Abbreviated | Title: Ph 2 | Olaparib in | Mesothelioma |
|--------------|-------------|-------------|--------------|
| Version Date | e: 02/24/20 | | |

| | | | | | Subsequent | | Post |
|---------------------------------|------------------------|-------------------------------|-------------|-------|------------|---|-------------|
| | | | Cyc | le 1 | Cycles | Treatment | Therapy |
| Procedure | Screening ¹ | Baseline | Day 1 | Day 8 | Day 1 | discontinuation visit ^{$\frac{2}{2}$} | Follow-up |
| $Urinalysis^2$ | Х | | Х | | | | |
| Coagulation ⁸ | Х | | Х | | | | |
| Serum or Urine hCG in | | | | | | | |
| women of childbearing | X | | Х | | Х | Х | |
| potential ⁹ | | | | | | | |
| Electrocardiogram ¹⁰ | Х | | Х | | | | |
| Sample collection for | | | | | | | |
| mutational analysis | | Х | | | | | |
| (mandatory) ¹¹ | | | | | | | |
| NIH 527 release form | | $\mathbf{X}^{\underline{12}}$ | | | | | |
| | | | | | | | |
| Correlative Research | | | Х | | Х | X | |
| Studies (See $5.1.2$) | | | | | | | |
| NIH Advance Directives | | Х | | | | | |
| Form ^{1.2} | | | | | | | |
| CT CAP (MRI if | | | Every 6 | | | | |
| appropriate); FDG-PET | X | | weeks \pm | | | \mathbf{X}^{14} | X 15 |
| | | | 7 days | | | | |
| Adverse Events | | | × | | | X | |
| Concomitant Madications | | | λ | | | | |
| CUIRCUIIIITAIIL INICUICATIVIIS | | | < | | | | |

- Screening evaluations are done within 28 days prior to enrollment with the exception of confirmation of diagnosis (within 6 months prior to enrollment) and ECG (within 7 days prior to enrollment) Ι.
- End of treatment visit will occur approximately 30 days after the last dose of study drug. If the patient is unable to return to the Clinical Center, symptom assessment may be performed via telephone and labs/scans may be performed by an outside provider; the research sample is not required in this circumstance. ¢i
- Include history of blood transfusion within previous 120 days from start of study treatment and the reasons e.g. bleeding or myelosuppression. S.
- These tests will be performed by the NIH CC Department of Laboratory Medicine. Additional analyses may be performed if clinically indicated. Any clinically significant abnormal laboratory values should be repeated as clinically indicated and recorded on the eCRF. 4.

| Olaparib in Mesothelioma | |
|--------------------------|------------------------|
| Abbreviated Title: Ph 2 | Version Date: 02/24/20 |

Full hematology assessments for safety: hemoglobin, red blood cells (RBC), platelets, mean cell volume (MCV), mean cell hemoglobin concentration [MCHC], mean cell hemoglobin (MCV), white blood cells (WBC), absolute differential white cell count (neutrophils, lymphocytes, monocytes, eosinophils and basophils) and absolute neutrophil count or segmented neutrophil count and Band forms should be performed at each visit and when clinically indicated. If absolute differentials not available please provide % differentials.

for bone marrow cellularity. If it is not possible to conduct cytogenetic analysis or flow cytometry on the bone marrow aspirate, then attempts should be made to carry out the tests on a blood sample. If findings are consistent with MDS/AML, study drug should be discontinued and a 3.3.1.3. Bone marrow analysis should include an aspirate for cellular morphology, cytogenetic analysis and flow cytometry, and a core biopsy full description of findings should be submitted to the manufacturer with an SAE report by the investigator. Presence or absence of blood Bone marrow or blood cytogenetic samples may be collected for patients with prolonged hematological toxicities as defined in Section cytogenetic abnormalities and flow cytometry will be documented on the clinical database.

- Biochemistry assessments for safety: sodium, potassium, calcium, magnesium, fasting glucose, creatinine, total bilirubin, gamma glutamyltransferase (GGT) – optional on C1D8, alkaline phosphatase (ALP), aspartate transaminase (AST), alanine transaminase (ALT), urea or blood urea nitrogen (BUN), total protein, albumin and lactic dehydrogenase (LDH). In case a subject shows an AST or ALT \ge 3xULN or total bilirubin ≥ 2 xULN please refer to Appendix D 'Actions required in cases of combined increase of Aminotransferase and Total Bilirubin – Hy's Law', for further instructions. ó
- Urinalysis by dipstick should be performed at screening/baseline and then only if clinically indicated. Microscopic analysis should be performed by the NIH Clinical Center Department of Laboratory Medicine if required. К.
- and if clinically indicated unless the patient is receiving warfarin. Patients taking warfarin may participate in this study; however, it is recommended that prothrombin time (INR and APTT) be monitored carefully at least once per week for the first month, then monthly if the Coagulation: activated partial thromboplastin time (APTT) and international normalized ratio (INR) will be performed at screening/baseline INR is stable. °.
- Two pregnancy tests on blood or urine samples will be performed for pre-menopausal women of childbearing potential one within 28 days Clinical Center Department of Laboratory Medicine. If results are positive the patient is ineligible/must be discontinued from the study. In prior to the start of study treatment and the other on Day 1 of the study prior to commencing treatment. Tests will be performed by the NIH the event of a suspected pregnancy during the study, the test should be repeated.
- copies of each of the timed 12-lead ECGs on each of the study days when they are collected. ECGs will be recorded at 25 mm/sec. All ECGs should be assessed by the investigator as to whether they are clinically significantly abnormal / not clinically significantly abnormal. If there is a clinically significant abnormal finding, the Investigator will record it as an AE on the eCRF. The original ECG traces must be stored in patient has been rested in a supine position for at least 5 minutes in each case. The Investigator or designated physician will review the paper ECGs are required within 7 days prior to starting study treatment and when clinically indicated. Twelve-lead ECGs will be obtained after the the patient medical record as source data 10.
- ^{*II*} Please refer to sections 5.1.2 and 5.3.

- As indicated in section 5.3.1, patients will be offered the opportunity to identify a designee to receive actionable genetic results. If the patient refuses, this must be documented in the medical record. 12.
- As indicated in section 12.3, all subjects \geq age 18 will be offered the opportunity to complete an NIH advance directives form. This should be done preferably at baseline but can be done at any time during the study as long as the capacity to do so is retained. The completion of the form is strongly recommended, but is not required. 13.
- Performed only if patient removed from study therapy for reason other than progressive disease 14.
- Follow up scans will continue every 6 weeks until disease progression. Scans performed outside the NIH Clinical Center are acceptable. 15.

